5.10. Concomitant and Prior Therapy

Concomitant medication will be summarized and compared between treatment groups using Fisher's exact test for the Randomized Population during the treatment period. The percentages of patients receiving each concomitant medication will be summarized by treatment using PT nested within Anatomical Therapeutic Chemical (ATC) Level 3 code. Medications will be ordered by decreasing frequency within ATC level.

A summary of previous diabetes therapies that were discontinued prior to informed consent will be generated for the Randomized Population. A summary of concomitant medication used during the lead-in period will also be provided for the Randomized Population.

5.11. Efficacy Analyses

5.11.1. Primary Outcome and Methodology

The primary objective of this study is to test the hypothesis that LY900014 is noninferior to Humalog on glycemic control (noninferiority margin [NIM]=0.4% for HbA1c) in patients 1 to <18 years of age with T1D, when administered as prandial insulin, in combination with basal insulin for 26 weeks. There will be 2 primary analysis methods, each tested at the full significance level of 0.05.

For the US FDA submission (using the ITT estimand), all randomized subjects, regardless of their postbaseline result availability, will be included in the analysis. Due to COVID-19, patients are allowed to have their laboratory data collected at a local laboratory if there is any ongoing extenuating situation, such as travel restriction. HbA1c data collected from the local laboratory will be included in the analysis in the same way as those collected from the central laboratory. The missing endpoints will be imputed by the copy reference or the return to baseline approach. For the copy reference approach, the reference for each treatment group is from the retrieved dropout patients who discontinue IP but have the measurement at the primary endpoint in the same treatment group. If there are only a limited number of patients in the reference group that leads to a failure in performing the proposed multiple imputation analysis such that the model cannot converge, or the number of records in the reference group is less than the number of records with missing data, the missing endpoints will be imputed by the return to baseline

approach. For the return to baseline approach, the patient-level observed baseline value plus a noise will be used to impute the missing endpoints. The noise follows a normal distribution with the variability estimated from the “washout HbA1c data.” The “washout HbA1c data” will be derived by subtracting the corresponding treatment mean at Week 26 from individual non-missing HbA1c values at Week 26. After imputation, the primary efficacy comparison will be based on the contrast between LY900014 and Humalog from an ANCOVA. The model for the change from baseline to the Week 26 HbA1c endpoint will include treatment and strata (pooled country, type of basal insulin, and age group) as fixed effects and baseline HbA1c as a covariate. The final estimates will be the combined estimates from at least 1000 imputations.

For non-FDA submissions, the primary efficacy comparison will be based on the contrast between LY900014 and Humalog at Week 26 (Visit 15) from the MMRM analysis of change from baseline in HbA1c including data collected from all randomized patients prior to permanent discontinuation of IP through Week 26 (efficacy estimand). In contrast to the population of ITT estimand, randomized patients with a baseline and at least one postbaseline result will be included in the analysis. The model for the analysis of the primary efficacy endpoint of change from baseline in HbA1c will include the fixed class effects of treatment, strata (pooled country, type of basal insulin, and age group), visit, and treatment-by-visit interaction, as well as the continuous, fixed covariates of baseline value. An unstructured covariance structure will be used to model the within-patient errors. Significance tests will be based on LS means and Type III tests. If this analysis fails to converge, the following covariance structures will be tested in order:

- Toeplitz with heterogeneity
- autoregressive with heterogeneity
- compound symmetry with heterogeneous variances
- Toeplitz
- autoregressive
- compound symmetry without heterogeneous variances

The first covariance structure that converges will be used. The Kenward-Roger approximation will be used to estimate denominator degrees of freedom.

For both primary analysis approaches, LY900014 will be declared noninferior to Humalog if the upper limit of the 2-sided 95% CI for the LS mean difference in the change from baseline in HbA1c for LY900014 minus Humalog is below +0.4%. In addition, the 95% CI for the treatment difference will be compared to an alternative NIM of +0.3%. Both estimands will be tested at the full significance level of 0.05.

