For the United States (US) Food and Drug Administration (FDA) submission (using the ITT estimand), the missing endpoints will be imputed by the copy reference approach. The reference for each treatment group is from the retrieved dropout patients who discontinue IP but have the measurement at the primary endpoint in the same treatment group. If there are only a limited number of patients in the reference group that leads to a failure in performing the proposed multiple imputation analysis such that the model cannot converge, or the number of records in the reference group is less than the number of records with missing data, the missing endpoints will be imputed by the patient-level observed baseline value plus a noise, assuming a washout of any potential treatment effect (or “return to baseline”). The noise follows a normal distribution, with the variability estimated from the “washout HbA1c data”. The “washout HbA1c data” will be derived by subtracting the corresponding treatment mean at Week 26 from individual non-missing HbA1c values at Week 26. After imputation, the primary efficacy comparison will be based on the contrast between LY900014 and Humalog from an analysis of covariance (ANCOVA). The model for the change from baseline to the Week 26 HbA1c endpoint will include treatment and strata (pooled country, type of basal insulin, and age group) as fixed effects and baseline HbA1c as a covariate. The final estimates will be the combined estimates from at least 1000 imputations.

For non-FDA submissions and publications, the primary efficacy comparison will be based on the contrast between LY900014 and Humalog at Week 26 (Visit 15) from the mixed-effect model repeated-measure (MMRM) analysis of change from baseline in HbA1c, including data collected from all randomized patients prior to permanent discontinuation of IP through Week 26 (efficacy estimand).

For both primary analysis approaches, LY900014 will be declared noninferior to Humalog if the upper limit of the 2-sided 95% confidence interval (CI) for the least-squares (LS) mean difference in the change from baseline in HbA1c for LY900014 minus Humalog is below +0.4%. In addition, the 95% CI for the treatment difference will be compared to an alternative NIM of +0.3%. Both estimands will be tested at the full significance level of 0.05.

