## 8. Discontinuation Criteria

### 8.1. Discontinuation from Study Treatment

In the event that a patient is discontinued from the study treatment, the investigator should encourage the patient to remain in the study for continued safety monitoring. If the patient decides to continue in the study without IP, no early termination procedures will be completed. Patients will continue study visits through the safety follow-up.

Lilly recognizes the importance of complete data collection. This study includes elements to minimize missing data. Randomized patients who are discontinued from IP before study completion are encouraged to remain in the study for continued monitoring. For patients who remain in the study after early discontinuation of IP, both efficacy (including HbA1c) and safety data will be collected at scheduled visits. The difference between stopping IP and discontinuing the study will be explained to patients as part of the informed consent, and patients will be encouraged to continue in the study even if they stop study drug. In addition, study site investigators will be trained on the importance of complete data collection, with additional re-education of sites and patients as necessary.

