### **10.3.3. Efficacy Analyses**

#### **10.3.3.1. Primary Analyses**

The primary objective of this study is to test the hypothesis that LY900014 is noninferior to Humalog on glycemic control (NIM=0.4% for HbA1c) in patients 1 to <18 years of age with T1D, when administered as prandial insulin (0 to 2 minutes prior to the meal), in combination with basal insulin for 26 weeks. There will be 2 primary analysis methods, each tested at the full significance level of 0.05.

For the US FDA submission (using the ITT estimand), the missing endpoints will be imputed by the copy reference approach. The reference for each treatment group is from the retrieved dropout patients who discontinue IP but have the measurement at the primary endpoint in the same treatment group. If there is only a limited number of patients in the reference group that leads to a failure in performing the proposed multiple imputation analysis such that the model cannot converge, or the number of records in the reference group is less than the number of records with missing data, the missing endpoints will be imputed by the patient-level observed baseline value plus a noise, assuming a washout of any potential treatment effect (or "return to baseline"). The noise follows a normal distribution with the variability estimated from the "washout HbA1c data". The "washout HbA1c data" will be derived by subtracting the corresponding treatment mean at Week 26 from individual non-missing HbA1c values at Week 26. After imputation, the primary efficacy comparison will be based on the contrast between LY900014 and Humalog from an ANCOVA. The model for the change from baseline to the Week 26 HbA1c endpoint will include treatment and strata (pooled country, type of basal

insulin, and age group) as fixed effects and baseline HbA1c as a covariate. The final estimates will be the combined estimates from at least 1000 imputations.

For non-FDA submissions and publications, the primary efficacy comparison will be based on the contrast between LY900014 and Humalog at Week 26 (Visit 15) from the MMRM analysis of change from baseline in HbA1c, including data collected from all randomized patients prior to permanent discontinuation of IP through Week 26 (efficacy estimand). The analysis model and selection of covariance structure are described in Section 10.3.1.

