5.11.3. Sensitivity Analyses for Missing Data

A missing-not-at-random-based analysis will be performed for both the efficacy and ITT estimands to assess sensitivity of departures from the missing-at-random (MAR) assumption. The tipping-point approach that will be used is similar to a progressive stress test (Ratitch et al. 2013). The basic idea is to impute the missing values and add a value (delta) to the imputed values of the experimental treatment group and perform an analysis for the primary endpoint on the delta-adjusted data set to see whether the conclusion of the primary analysis is overturned. If not, a larger delta is chosen and the process repeated until the primary result is overturned. If the delta required to overturn the primary result is not a plausible departure from MAR, then the primary result is robust to plausible departures from MAR. The initial delta is set to 0.1 with an increment of 0.1. Imputation under the noninferiority null method (where delta equals the NIM=0.4) will be included as a special case of the progressive stress test.

For the ITT estimand, the imputation of missing data will be as described for the FDA primary analysis, and ANCOVA on the change from baseline to Week 26 in HbA1c will be used.

For the efficacy estimand, the copy reference approach will be used to impute missing data and the reference group will be the Humalog treatment group. Imputation will be for all longitudinal visits.

Sensitivity Analyses for Missing Data due to COVID-19 pandemic:

Missing data due to the pandemic represents an extraordinary circumstance, and missing data could be more prevalent in some geographic regions than in others. Lilly has been following a mitigation plan that aims to reduce the impact from the pandemic. Nevertheless, Lilly expects missing data at the primary endpoint visit, Visit 15 HbA1c, for COVID-19 related reasons:

- COVID-19 infection (adverse event) or death caused by infection,
- Discontinuation of treatment due to COVID-19 related reasons,
- Discontinuation of study due to COVID-19 related reasons, and
- Completed the 26 week treatment period, but missed primary endpoint due to COVID-19 related reasons.

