5.11.4. Analysis of Gated Objectives

Gatekeeping strategy will be used to control the overall type I error for testing the following gated objectives: noninferiority of LY900014+20 to Humalog in change from baseline to the study primary endpoint in HbA1c and superiority of LY900014 compared with Humalog in change from baseline to the study primary endpoint in HbA1c.

Following the successful claim of the primary objective, the noninferiority between LY900014+20 and Humalog in HbA1c change from baseline will be assessed using the same approach for the primary objective (ITT estimand for FDA submission and efficacy estimand for non-FDA submissions) with a NIM of 0.4%. Only when the noninferiority between LY900014+20 and Humalog is demonstrated, the superiority of LY900014 in controlling HbA1c compared to Humalog will be assessed. The superiority assessment will be based on the above statistical approaches for the primary objective (ITT estimand for FDA submission and efficacy estimand for non-FDA submissions). If the upper limit of the 2-sided 95% CI is below zero, LY900014 will be declared superior to Humalog.

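### Does the return-to-baseline fallback in the FDA (ITT) analysis need a smaller noise SD?

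*SAP*

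**What the plan says.** SAP section 5.11.1 first tries to impute missing Week 26 HbA1c from retrieved dropouts in the same arm. It switches to return to baseline if that model fails to converge or if "the number of records in the reference group is less than the number of records with missing data". Under the switch, "the patient-level observed baseline value plus a noise will be used to impute the missing endpoints". The noise is normal, and its variability is estimated from data "derived by subtracting the corresponding treatment mean at Week 26 from individual non-missing HbA1c values at Week 26". Only the arm mean is removed, not the patient's baseline. The completed data go into an ANCOVA adjusted for baseline HbA1c and are combined over at least 1000 imputations.

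The protocol gives the same rule in the Synopsis ("the missing endpoints will be imputed by the patient-level observed baseline value plus a noise") and in section 10.3.3.1, which adds the rationale: "the missing endpoints will be imputed by the patient-level observed baseline value plus a noise, assuming a washout of any potential treatment effect". Neither document explains the choice of SD.

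The rule reaches beyond the primary test. SAP section 5.11.3 reuses it in the tipping-point analysis ("For the ITT estimand, the imputation of missing data will be as described for the FDA primary analysis"), and section 5.11.4 carries the primary methods to both gated tests ("ITT estimand for FDA submission and efficacy estimand for non-FDA submissions"). The MMRM for the efficacy estimand does not use it.

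**The concern.** Between-patient spread seems to enter twice: once through the baseline that is carried forward, and again through noise with the full Week 26 SD. Call that SD s and the baseline-to-Week 26 correlation r. Given baseline, an imputed record has variance s², while an observed record has (1 − r²)s². Any nonzero r therefore makes imputed records noisier than observed ones.

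If the fallback is used, the confidence interval for the FDA noninferiority test widens, as do those for the gated LY900014+20 and superiority tests. The sponsor would lose power for no visible reason, and replacing the SD by the ANCOVA residual SD looks like a one-line repair.

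A second gap sits beside it. The reference group is defined by arm, but the text does not say whether a trigger in one arm moves the other arms to the fallback.

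**Working it through.** **The plan's own power (protocol section 10.1).** SD 1.1%, 240 completers per blinded arm: SE = 1.1 × √(2/240) = 0.1004.
- Margin 0.4: Φ(0.4/0.1004 − 1.96) = 97.8% (stated: above 95%).
- Margin 0.3: 84.8% (stated: above 80%).
- LY900014+20, true difference 0.07, 240 against 120: SE = 1.1 × √(1/240 + 1/120) = 0.1230, and Φ(0.33/0.1230 − 1.96) = 76.5% (stated: about 76%).
- 240/0.85 and 120/0.85 round up to 283 and 142, and 283 + 283 + 142 = 708.

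All of these reproduce.

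**Inputs not in the documents (assumed).** r from 0.5 to 0.85; a missing fraction m of 5% to 15%; equal SDs at baseline and Week 26. Planned dropout is 15%, but protocol section 8.1 says that after IP is stopped "both efficacy (including HbA1c) and safety data will be collected at scheduled visits", so 15% truly missing is an upper case.

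**Effect on the SE.** With many imputations, Rubin's total variance is about T = (1/n₁ + 1/n₂)[(1 − m)(1 − r²)s² + 2m·σ²], where σ² is the noise variance. As written, σ² = s²; with residual noise, σ² = (1 − r²)s². The SE ratio is √{[(1 − m)(1 − r²) + 2m] / [(1 + m)(1 − r²)]}. For r = 0.7 and m = 0.15 this is √(0.7335/0.5865) = 1.118.

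| m | r = 0.5 | r = 0.6 | r = 0.7 | r = 0.8 |
|---|---|---|---|---|
| 5% | 1.016 | 1.026 | 1.045 | 1.081 |
| 15% | 1.043 | 1.071 | 1.118 | 1.210 |

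Simulation agrees. With s = 1.1, 283 per arm, r = 0.7 and 15% missing, the Rubin SE is 0.0799 as written and 0.0715 with residual noise. The upper limit moves by 1.96 × (0.0799 − 0.0715) = 0.016 HbA1c points. The actual SD of the estimate is about 0.060 to 0.063, so part of the excess comes from using Rubin's rules with this kind of imputation and would survive the smaller noise.

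**The benchmark is a choice.** Return to baseline centres on the patient's own baseline. The spread around that centre is the SD of change, s√(2(1 − r)), not the residual SD around a regression line with slope r. Against the SD of change, the plan's noise is exactly right at r = 0.5 and too small below it. At r = 0.7 the excess in the SE is √(0.5845/0.5445) − 1 = 3.6% at 5% missing and √(0.7335/0.6135) − 1 = 9.3% at 15%.

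**Behaviour at the noninferiority boundary.** Take a true difference of 0.4 and missing patients who resemble observed ones. Imputed changes centred on zero in both arms shrink the mean estimate to (1 − 0.15) × 0.4 = 0.34 at 15% missing. For r = 0.7, with Rubin SE 0.0805 and empirical SD 0.0624, the chance of declaring noninferiority is about Φ[(0.06 − 1.96 × 0.0805)/0.0624] = Φ(−1.57) = 5.9%. With residual noise the SE is 0.0805/1.117 = 0.0721, giving Φ(−1.30) = 9.6%. Simulated rates (2000 trials per cell, s = 1.1, nominal 2.5%):

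| r | m | As written | Residual SD |
|---|---|---|---|
| 0.5 | 5% | 2.9% | 3.4% |
| 0.5 | 15% | 5.1% | 6.7% |
| 0.7 | 5% | 2.9% | 3.8% |
| 0.7 | 15% | 5.3% | 9.9% |
| 0.85 | 5% | 2.8% | 5.2% |
| 0.85 | 15% | 4.7% | 17.8% |

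Repeat runs at r = 0.7 and 15% missing gave 5.5% and 6.1% as written, against 9.5% and 9.7%. If patients with missing data truly wash out, the diluted difference is the target and the rate stays below 2.5% with either SD.

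**Power as written, 15% missing.** The least favourable simple reading takes 1.1% as the SD of change. For r = 0.5/0.6/0.7/0.8, direct simulation gives 94/92/88/80% at margin 0.3 and 91/87/81/73% for LY900014+20. Putting the Rubin SE into Φ(d/SE − 1.96), where d is the distance from the true difference to the margin, gives lower figures, because it treats an over-wide SE as the sampling SD.

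**The case for a change.** The strongest case for acting is that the fallback is a live route. SAP section 5.11.3 expects Visit 15 values lost to COVID-19, including in patients who completed treatment. They add to the missing count but not to the retrieved dropouts, so the count-based trigger becomes more likely. If the wide noise is meant to offset the bias toward no difference, the plan does not say so. As an offset it is also poorly aimed: error still exceeds 2.5% in the cases above, and the size of the offset depends on r, which has nothing to do with the bias. The explicit tool, imputation with delta equal to the margin, is planned only as a sensitivity analysis. And a rule left open by arm could let the primary contrast mix two missing-data assumptions, chosen after the data are seen.

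Most of this stands as description: the SE is over-wide when the fallback is used, and the reason for the SD is not written down. It does not support the smaller SD. Reducing the noise alone raises the risk of false noninferiority where missing patients resemble observed ones, and no benchmark SD is clearly right. The arm-level point is a real omission, but a statistician programming the analysis would put all arms on one rule, so that the contrast compares like with like. Such a decision needs no arm-level results.

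**Conclusion.** No change is needed. The noise SD exceeds the baseline-adjusted residual SD for any nonzero r, and the SD of change only for r above 0.5. The cost is an SE about 2-4% too large at 5% missing and about 4-12% at 15%, relative to residual noise, for assumed r of 0.5 to 0.7. It falls only on the FDA (ITT) analysis, and only if the fallback is triggered. No shortfall against the stated powers is shown, except possibly for LY900014+20 at r near 0.8 with 15% missing (73% against about 76%).

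The fallback as a whole is not conservative for noninferiority, and that is the reason to leave the noise alone. The wide noise partly offsets the pull toward zero, and cutting it in isolation would trade a little precision for roughly 5-6% against 10% false noninferiority at r = 0.7 and 15% missing. That comparison assumes missing patients behave like observed ones; under true washout neither SD exceeds 2.5%. What remains is a fair trade-off in the SD and two unstated details, the reason for it and the reach of a trigger across arms, which analysts can settle sensibly.

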Unless otherwise noted, all tests of treatment effects will be conducted at a 2-sided alpha level of 0.05, and CIs will be calculated at 95%, 2-sided. All tests of interactions between treatment groups and other factors will be conducted at a 2-sided alpha level of 0.10. Countries in similar geographic regions with fewer than 10 patients, based on all randomized population, will be pooled to achieve a pooled country of at least 10 patients. All analyses using country in the model will use a pooled country, unless otherwise specified. The final pooling by country and geographic region will be finalized prior to data lock.

Baseline is defined as the last non-missing measurement at or before the randomization visit (Visit 4), unless otherwise specified.

A restricted maximum likelihood-based, mixed-effect model repeated-measure (MMRM) analysis will be used to analyze continuous longitudinal variables. All the longitudinal observations at each scheduled postbaseline visit will be included in the analysis. The model for

the analysis of the primary efficacy endpoint of change from baseline in HbA1c will include the fixed class effects of treatment, strata (pooled country, type of basal insulin, and age group), visit, and treatment-by-visit interaction, as well as the continuous, fixed covariate of baseline value. For analyses of variables other than HbA1c, the HbA1c stratum ( $\leq 8.0\%$ ,  $> 8.0\%$ ) will be included in the model. An unstructured covariance structure will be used to model the within-patient errors. Significance tests will be based on least-squares (LS) means and Type III tests. SAS PROC MIXED will be used to perform the analysis. If this analysis fails to converge, the following covariance structures will be tested, in order:

- Toeplitz with heterogeneity
- Autoregressive with heterogeneity
- Compound symmetry with heterogeneous variances
- Toeplitz
- Autoregressive
- Compound symmetry without heterogeneous variances.

The first covariance structure that converges will be used. The Kenward-Roger approximation will be used to estimate denominator degrees of freedom.

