#### **10.3.3.2. Secondary Analyses**

Following the successful claim of the primary objective, the assessment of noninferiority between LY900014+20 and Humalog and superiority between LY900014 and Humalog in

controlling HbA1c will use gatekeeping strategy. The noninferiority between LY900014+20 and Humalog will be evaluated first with the significant level of 0.05 (from the primary objective). Once the noninferiority is achieved, the superiority test between LY900014 and Humalog will be performed with the significant level of 0.05 (from the gated noninferiority objective). Both the assessments will be based on the analysis approaches used for the primary objective (ITT estimand for FDA submission and efficacy estimand for non-FDA submissions).

HbA1c and change from baseline in HbA1c at all timepoints will be analyzed by the same MMRM model used for the primary analysis for the efficacy estimand. The noninferiority in change from baseline in HbA1c for LY900014+20 to Humalog will be based on the same model.

Additional continuous secondary efficacy variables, as well as the change from baseline for these variables, will be analyzed either by the MMRM or ANCOVA models described in Section 10.3.1 for the efficacy estimand.

Treatment comparisons for the proportion of patients with HbA1c < 7.0% and < 7.5% will be analyzed using a longitudinal logistic regression with repeated measurements conducted by a generalized linear mixed model including independent variables of treatment, baseline HbA1c value, visit, baseline HbA1c by visit interaction, and treatment by visit interaction. An unstructured covariance structure will be used. As a sensitivity analysis, the proportion of patients with HbA1c < 7.0% and < 7.5% at Week 26 (Visit 15), imputed using LOCF, will be compared using a logistic regression model including treatment and baseline HbA1c value in the model.

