- For the 7-point self-monitored blood glucose (SMBG) profiles, the profiles measured after the first IP dose date and prior to the last IP dose date will be considered as data on IP.

Unless otherwise noted, all tests of treatment effects will be conducted at a 2-sided alpha level of 0.05, and confidence interval (CI) will be calculated at 95%, 2-sided. All tests of interactions between treatment groups and other factors will be conducted at a 2-sided alpha level of 0.05. Countries in similar geographic regions with fewer than 10 patients, based on all Randomized Population, will be pooled to achieve a pooled country of at least 10 patients. All analyses using country in the model will use a pooled country, unless otherwise specified. The final pooling by country and geographic region will be finalized prior to data lock.

[Table ITSB.5.2](#) shows the definition of baseline and post-baseline for each variable to be analyzed. The baseline variables are derived from the evaluable data during the baseline period.

Table ITSB.5.2. Baseline and Postbaseline Definitions and Patient Population by Study Period and Type of Analysis

Study Period/Analysis	Patient Population	Baseline Observations	Post-Baseline Observations
Lead-In Period			
HbA1c ANCOVA	All Randomized Patients	Visit 1	Visit 4 prior to initiation of IP
Basal, bolus, and total insulin doses, and bolus/total insulin dose ratios continuous analysis	All Randomized Patients	Not applicable	Visit 3-4
TEAE	All Enrolled Patients	Prior to first dose of open-label insulin lispro (or Visit 2 date if the dose date is missing)	The entire lead-in period after first dose of open-label insulin lispro and prior to the first dose of IP (or Visit 4 if the dose date is missing)
26-Week Treatment Period (including Safety Follow-Up Visit where applicable)			
HbA1c ANCOVA (ITT estimand)	All Randomized Patients	Last of Visits 1-4	Visit 15 with imputation for patients who discontinue study prior to Visit 15
HbA1c MMRM (efficacy estimand)	All Randomized Patients with a baseline and at least one post-baseline observation while on IP	Last of Visits 1-4	Visits 7, 10, and 15 prior to discontinuation of IP
HbA1c categorical analysis longitudinal logistic regression	All Randomized Patients with a baseline and at least one post-baseline observation while on IP	Last of Visits 1-4	Visits 7, 10, and 15 prior to discontinuation of IP

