5.11.5. Other Secondary Efficacy Analyses

The analyses described in Section 5.11.5 to Section 5.11.7 will include data collected from all randomized patients prior to permanent discontinuation of IP.

The longitudinal observations of actual and change from baseline in HbA1c up to Week 26 will be analyzed using the same MMRM model as for the analysis of the primary outcome.

At each visit (including both telephone and office visits), the basal daily dose and prandial insulin dose at different time points (morning meal, mid-day meal, evening meal and other) taken 3 days prior to the visit will be collected in eCRF. The average daily basal insulin dose per visit for each patient will be used in the analysis. Similarly, the average prandial insulin dose for each meal category (ie, morning meal, mid-day meal, evening meal, snack, and other) will be calculated, and average daily prandial insulin dose calculated as the sum of these average prandial insulin meal doses will be used for analysis. If either average daily basal or average daily prandial insulin dose is missing, the total daily insulin dose and the prandial/total insulin dose ratio will be set as missing for analysis. The analyses of insulin dose (ie, actual and change from baseline in total, basal, prandial insulin dose and prandial/total insulin dose ratio), will use an MMRM model similar to that for the primary outcome with an additional term of HbA1c stratum ($\leq 8.0\%$, $> 8.0\%$).

Treatment comparisons for the proportion of patients with HbA1c $< 7.0\%$ and $< 7.5\%$ will be analyzed using a longitudinal logistic regression with repeated measurements conducted by a generalized linear mixed model including independent variables of treatment, baseline HbA1c value, visit, baseline HbA1c-by-visit interaction, and treatment-by-visit interaction. An unstructured covariance structure will be used. As a sensitivity analysis, the proportion of patients with HbA1c $< 7.0\%$ and $< 7.5\%$ at Week 26 (Visit 15), imputed using LOCF, will be compared using a logistic regression model with terms for treatment and baseline HbA1c value.

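### The efficacy-estimand MMRM fits one baseline HbA1c slope across Weeks 6, 12 and 26, which costs some precision at Week 26 if that slope changes between visits

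*SAP*

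**What the plan says.** The MMRM for change from baseline in HbA1c is the primary analysis for non-FDA submissions. SAP Section 5.11.1 lists its terms as treatment, the strata (pooled country, type of basal insulin, age group), "visit, and treatment-by-visit interaction, as well as the continuous, fixed covariates of baseline value". Protocol Section 10.3.1 and the synopsis give the same model, with baseline entering "as well as the continuous, fixed covariate of baseline value". The plural in the SAP adds no second term; no interaction with baseline is named in either document.

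According to SAP Table ITSB.5.2 (Section 5.1), the model uses "Visits 7, 10, and 15 prior to discontinuation of IP", which the Schedule of Activities places at Weeks 6, 12 and 26. On covariance, the SAP states: "An unstructured covariance structure will be used to model the within-patient errors". The HbA1c stratum is left out of this model because continuous baseline HbA1c takes its place (SAP Section 5.2), so the single slope is the only adjustment for baseline glycemia.

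The longitudinal logistic model for HbA1c below 7.0% and 7.5% uses the same three visits. In SAP Section 5.11.5 it includes "visit, baseline HbA1c-by-visit interaction, and treatment-by-visit interaction", and protocol Section 10.3.3.2 agrees: "baseline HbA1c by visit interaction, and treatment by visit interaction". Neither document explains the difference.

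**The concern.** The Week 26 contrast from this MMRM decides noninferiority of LY900014 and, through the gatekeeping sequence (SAP Sections 5.5 and 5.11.4), noninferiority of LY900014+20 and then superiority. The unstructured covariance lets variances and correlations differ by visit, but the dependence on baseline may not.

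Protocol Section 5.4 gives a reason why it might. Prandial titration is emphasized in the first 12 weeks so that Week 26 HbA1c reflects a more stable period. Week 6 therefore falls within titration and Week 26 after it. If change depends more strongly on baseline at Week 26 than earlier, a slope pooled over the three visits is pulled towards the earlier ones. It then adjusts too little at the visit that matters, and the confidence interval there is wider than it needs to be.

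**Working it through.** **Step 1. Reproduce the planned power.** Inputs, from protocol Section 10.1: SD 1.1%; 240, 240 and 120 completers; true difference 0 for the blinded pair and 0.07% for LY900014+20; margin 0.4% (alternative 0.3%). Tests are at two-sided 5%.

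SE = SD × √(1/n₁ + 1/n₂); power = Φ((margin − difference)/SE − 1.96).

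- Blinded pair: SE = 1.1 × √(2/240) = 0.1004. Margin 0.4%: Φ(3.98 − 1.96) = 97.8% (plan: above 95%). Margin 0.3%: Φ(2.99 − 1.96) = 84.8% (plan: above 80%).
- LY900014+20: SE = 1.1 × √(1/240 + 1/120) = 0.1230. Φ(0.33/0.1230 − 1.96) = 76.5% (plan: about 76%).

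All three agree with the plan.

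**Step 2. Cost of a common slope.** Let b₆, b₁₂ and b₂₆ be the slopes of change on baseline at the three visits, g the common slope, σ²_B the baseline variance and S the Week 26 residual variance. With visit-specific slopes the variance at Week 26 is S. With a common slope it is S + (b₂₆ − g)²σ²_B. Hence

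SE ratio = √(1 + (b₂₆ − g)²σ²_B / S),

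where g = (1′V⁻¹b)/(1′V⁻¹1), the generalized-least-squares limit, and V is the residual covariance over the three visits (large sample, complete data).

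The documents give none of these quantities. I assume equal SDs at all visits, scaled to 1, so that bₜ = ρₜ − 1 and the residual variance is 1 − ρₜ², where ρₜ is the correlation with baseline. The residual correlation between visits is 0.5, varied from 0.3 to 0.7 in the last column.

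Example, ρ = 0.85/0.75/0.65: g = −0.192 and S = 1 − 0.65² = 0.5775, so the ratio is √(1 + 0.158²/0.5775) = √1.043 = 1.021.

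| ρ at Weeks 6/12/26 | Slopes | g | SE ratio | Range |
|---|---|---|---|---|
| 0.70/0.70/0.70 | −0.30/−0.30/−0.30 | −0.300 | 1.000 | 1.000 |
| 0.80/0.75/0.70 | −0.20/−0.25/−0.30 | −0.236 | 1.004 | 1.003–1.006 |
| 0.85/0.75/0.65 | −0.15/−0.25/−0.35 | −0.192 | 1.021 | 1.017–1.033 |
| 0.90/0.80/0.70 | −0.10/−0.20/−0.30 | −0.125 | 1.029 | 1.022–1.045 |
| 0.90/0.80/0.60 | −0.10/−0.20/−0.40 | −0.115 | 1.062 | 1.048–1.089 |

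**Step 3. Effect on power if 1.1% is the residual SD.** Multiply the SEs of Step 1 by the ratio. I use 1.021 for a moderate decline and 1.061 for a steep one.

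| SE ratio | Blinded, 0.4% | Blinded, 0.3% | LY900014+20, 0.4% |
|---|---|---|---|
| 1.000 | 97.8% | 84.8% | 76.5% |
| 1.004 | 97.8% | 84.5% | 76.2% |
| 1.021 | 97.4% | 83.3% | 74.8% |
| 1.061 | 96.4% | 80.4% | 71.5% |

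As an outer case, slopes of −0.10/−0.30/−0.60 with a baseline SD of 1.0% raise the Week 26 variance by 5% to 25%. That costs at most 3.3, 8.6 and 9.6 points in the three columns.

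**Step 4. If 1.1% is an unadjusted SD.** The Week 26 variance is then 1.21 − b₂₆²σ²_B + (b₂₆ − g)²σ²_B. Take b₂₆ = −0.40, g = −0.12 and σ_B = 1.0: 1.21 − 0.16 + 0.078 = 1.128. This is below the planned 1.21, so power exceeds the plan. Visit-specific slopes would give 1.05, so the difference is a gain not taken.

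**Step 5. Simulation.** The MMRM was simulated with 283 per arm and 15% random monotone dropout. The SE ratio was 1.000 with equal slopes, 1.022 with moderate divergence (−0.15/−0.25/−0.40) and 1.086 with strong divergence. In the two unequal-slope cases, bias with the common slope was at most 0.002% HbA1c and coverage was 94% to 94.5%.

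**The case against.** The strongest reply is that nothing in the documents shows the slopes to be unequal. The loss is zero if they are equal, and the slope of change depends on the SD at each visit as well as on the correlation. With ρ = 0.90/0.80/0.70 but post-baseline SDs rising to 1.15 times baseline, the inflation is only about 0.5%. This stands: the loss is conditional, and its range starts at zero.

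Other points also stand. The model is fully prespecified, and randomization stratified by HbA1c limits chance imbalance. The FDA primary analysis (ITT ANCOVA) and the LOCF ANCOVA of SAP Section 5.11.2 are single-endpoint models with their own baseline slope, so neither is affected.

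Three stronger readings are tempting, and the documents support none of them.

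- *The trial forfeits a fixed share of its sample size.* Squaring 1.021 and 1.061 gives about 4% to 13% more variance, but that counts only the moderate and steep cases.
- *The Week 26 estimate is biased.* Under random dropout the bias was negligible. A bias of about 0.06% to 0.10% (about 0.01% with visit-specific slopes) appeared only when dropout was assumed to depend on baseline in opposite directions by arm. Nothing in the plan suggests that pattern.
- *The responder model contradicts the primary model.* It is a logistic model that also omits the strata, and neither document says that the two must match. It shows only that the sponsor was willing to fit the term on these visits.

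**Conclusion.** The point holds as a conditional efficiency improvement. One slope is fitted to three visits that span titration and the later, more stable phase. If the slopes differ, precision is lost at Week 26. The planned analysis remains valid under random dropout.

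The likely size is small. With equal SDs and a residual correlation of 0.5, the SE rises by between 0% and about 6% across the patterns in Step 2, and the steep case ranges from about 5% to 9% with the residual correlation. The consequence is greatest for LY900014+20. That comparison has the lowest planned power, and superiority is tested only if it succeeds. The primary blinded comparison at the 0.4% margin has ample reserve at inflation of 2.1% to 6.1%. Whether any of this is a shortfall against the plan depends on whether 1.1% is a residual or an unadjusted SD, which protocol Section 10.1 does not say.

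**What to change.** Add a baseline HbA1c-by-visit interaction to the primary MMRM in SAP Section 5.11.1, protocol Section 10.3.1 and the synopsis. Carry it into the models that reuse this MMRM: the gated tests (SAP Section 5.11.4), the Per Protocol and Completer analyses (5.11.2), the efficacy-estimand HbA1c subgroup models (5.13.1) and the HbA1c model by TEADA status (5.12.7.1). If the sponsor prefers the present model, one sentence should justify the constant slope.

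The cost is two parameters with about 600 expected completers and a wording change. No new data are needed, and the loss is negligible if the slopes prove equal. The change should be made before treatment assignments are unblinded.
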